4.5.9.5 Plans for Interim Analyses

No interim analyses for the purpose of stopping early are planned for this study.

4.5.9.6 Handling of Missing Data

All summaries will be performed only on subjects undergoing the scheduled procedure and only observed data will be summarized. There will be no imputation of data for early terminated subjects or for missing data within the database.

4.5.9.7 Subgroup Analyses

Subgroup analyses are planned to be performed for the subgroup of subjects who have a medical history of treatment for cancer (e.g. chemotherapy or radiation) and may be performed for additional groups pending the distributions of baseline demographic or clinical characteristics. These analyses will be exploratory and summary statistics for the procedure-related parameters will be provided for each subgroup.

5.0 ADVERSE EVENTS

5.1 DEFINITIONS

5.1.1 Adverse Event

An AE is defined as any untoward medical occurrence. An untoward medical occurrence includes any new, undesirable medical experience or worsening of a pre-existing condition, which occurs throughout the duration of the clinical study.

In this study, an AE is defined as any undesirable clinical occurrence in a subject that may be attributable to the study procedures or the ENSEAL X1 device. Only AEs attributable to the study procedures or the ENSEAL X1 device are to be recorded in the eCRF and reported to the Sponsor.

5.1.2 Serious Adverse Event

It is the Investigator's responsibility to determine the "seriousness" of a reportable AE.

A SAE is defined as an AE (as defined in Section 5.1.1) that results in any of the following:

- Death;
- A life-threatening illness or injury;
- A permanent impairment of a body structure or a body function;
- Required in-patient hospitalization or prolongation of existing hospitalization;
- Resulted in medical or surgical intervention to prevent life-threatening illness or injury or permanent impairment to a body structure or a body function;
- Led to a fetal distress, fetal death, or a congenital abnormality or birth defect.

Note: "Death" should not be reported as an AE. The cause of death should be reported as the AE. The only exception is "Sudden Death" when the cause is unknown.

Note: Planned hospitalization for a pre-existing condition, or a procedure required by the protocol, without serious deterioration in health, is not considered a SAE.

5.1.3 Severity of Adverse Events

It is the Investigator's responsibility to assess the severity of an AE. A change in severity may constitute a new reportable AE.

The following guideline should be used to determine the severity of each AE:

- **MILD:** A type of AE that is usually transient and may require only minimal treatment or therapeutic intervention. The event does not generally interfere with usual activities of daily living.
- **MODERATE:** A type of AE that is usually alleviated with additional specific therapeutic intervention. The event interferes with usual activities of daily living, causing discomfort but poses no significant or permanent risk of harm to the research participant.
- **SEVERE:** A type of AE that interrupts usual activities of daily living, or significantly affects clinical status, or may require intensive therapeutic intervention.

5.1.4 Relationship of Adverse Events

It is the Investigator's responsibility to assess the relationship of a reportable AE (as defined in Section 5.1.1). Only AEs attributable (relationship of unlikely, possible, probable, causal relationship) to the study procedures or the ENSEAL X1 device are to be

recorded in the eCRF and reported to the Sponsor.

The following guidelines should be used in determining the relationship of an AE in the study:

- **Not related** – Relationship to the procedures or device can be excluded when:
 - The event is not a known side effect of the product category the device belongs to or of similar devices and procedures;
 - The event has no temporal relationship with the use of the device or the procedures;
 - The event does not follow a known response pattern to the device (if the response pattern is previously known) and is biologically implausible;
 - The discontinuation of the device application or the reduction of the level activation/exposure (when clinically feasible) and reintroduction of its use (or increase of the level of activation/exposure), does not impact on the event;
 - The event involves a body-site or an organ not expected to be affected by the device or the procedure;
 - The event can be attributed to another cause (e.g. an underlying or concurrent illness/clinical condition, an effect of another device, drug, treatment, or other risk factors);
 - Harms to the subject are not clearly due to use error; or
 - To establish the non-relatedness, not all the criteria listed above might be met at the same time, depending on the type of device/procedure and the event.
- **Unlikely** – The relationship with the use of the device seems not relevant and/or the event can be reasonably explained by another cause, but additional information may be obtained.
- **Possible** – The relationship with the use of the device is weak but cannot be ruled out completely. Alternative causes are also possible (e.g. an underlying or concurrent illness/condition and/or an effect of another device, drug, or treatment). Cases where relatedness cannot be assessed or no information has been obtained should also be classified as possible.
- **Probable** – The relationship with the use of the device seems relevant and/or the event cannot reasonably be explained by another cause, but additional information may be obtained.
- **Causal relationship** – The event is associated with the device or with procedures beyond reasonable doubt when:
 - The event is a known side effect of the product category the device belongs to or of similar devices and procedures;
 - The event has a temporal relationship with the device uses/application or procedures;
 - The event involves a body-site or organ that:
 - The device or procedures are applied to;

- The device or procedures have an effect on;
 - The event follows a known response pattern to the medical device (if the response pattern is previously known);
 - The discontinuation of medical device application (or reduction of the level of activation/exposure) and reintroduction of its use (or increase of the level of activation/exposure), impact on the event (when clinically feasible);
 - Other possible causes (e.g. an underlying or concurrent illness/clinical condition and/or an effect of another device, drug, or treatment) have been adequately ruled out;
 - Harm to the subject is due to error in use; or
 - To establish the relatedness, not all the criteria listed above might be met at the same time, depending on the type of device/procedure and the event.

5.1.5 Pre-existing Condition vs. Adverse Event

A pre-existing condition is defined as a medical condition that is present before the performance of the study procedure. Pre-existing conditions are to be reported as part of the subject's medical history. Worsening of a pre-existing condition while on study may be considered an AE.

5.2 REPORTING PROCEDURES FOR ADVERSE EVENTS

5.2.1 Recording Adverse Events

The Investigator will record all AEs (both AEs and SAEs) considered attributable (relationship of unlikely, possible, probable, causal relationship) to the study procedure or the ENSEAL X1 in the source documents and eCRF.

Standard medical terminology should be used when recording AEs. In addition, the following information should be recorded:

- Onset date;
- Resolution date or date of death;
- Severity of the event;
- Indication of whether the event is serious;
- Relationship of AE to the device used in the study;
- Relationship of AE to the study procedure;
- Action taken;
- Event status; and
- Was the event anticipated or not.

Data related to SAEs will be collected until the event resolution, or until the event is considered stable, or until all attempts to determine the resolution of the event are exhausted. All SAEs that are unresolved at study completion (or at the last visit completed for early withdrawal subjects) will be recorded as ongoing at study end.

5.2.2 Reporting Adverse Events

The Investigator is required to report AEs to the Sponsor experienced by subjects who provided informed consent to the Sponsor within two weeks from when they became aware of the event. All AEs must be reported on the AE eCRF and be documented throughout the clinical investigation.

5.2.3 Reporting Serious Adverse Events

Any AE that the Investigator determines to be a SAE must be reported by the study site within 72 hours of becoming aware of the event to the Sponsor by completing the SAE eCRF. A notification containing the pertinent data will be automatically generated by the EDC system and forwarded to the Sponsor. Supporting SAE documentation should be de-identified and emailed to the Clinical Study Lead.

The Investigator will be required to assess if the SAE is considered anticipated (Appendix IV) and if the event involved a product complaint. The report of an SAE by a study site does not constitute an admission that study personnel or the user facility (hospital/clinic) caused or contributed to the event. The study site is also responsible for submitting to the reviewing IRB/EC per their IRB/EC procedures.

5.3 SAFETY MONITORING

If any serious and unexpected AEs occur during the study, all PIs will be notified by the Sponsor within 10 days of learning of the event.

6.0 PRODUCT COMPLAINTS

A product complaint is any written, electronic, or oral communication that alleges deficiencies related to the identity, labeling, quality, durability, reliability, safety, effectiveness, or performance of a device after it is released for distribution. A product complaint may or may not be associated with an AE/SAE.

6.1 REPORTING PRODUCT COMPLAINTS FOR MARKETED DEVICES

All product complaints related to devices in the procedure shall be documented throughout the clinical investigation. Product complaints related to an Ethicon-manufactured ENSEAL X1 must be reported to the Sponsor in a timely manner and no later than 24 hours after becoming aware of the event. When a sponsor representative becomes aware of a product complaint, the Product Complaint Team must be notified within 24 hours after becoming aware of the event. The Product Complaint Form must be emailed to the Sponsor Customer Complaint team at the following email address:

The sites will report Product Complaints by completing the Product Complaint Form (PCF). If a product complaint is related to an AE, the site must complete an AE eCRF as well. The site will indicate on the PCF if this complaint is related to an AE and provide the description. One copy of the processed form should be kept on-site and the device should be retained. Sponsor representatives will organize collection of the device for evaluation as needed.

APPENDIX I – VESSEL SEALING ASSESSMENT

Table 1 Tissue Sticking	
Score	Description
1	No sticking
2	Slight sticking requiring activation of study device to release tissue
3	Tissue sticking requiring counter-tension to gently grasp and remove tissue
4	Tissue sticking requiring counter-tension and extensive force to remove tissue or such that tissue is damaged or torn during removal process

Comments:

APPENDIX II – DEVICE PROCEDURE QUESTIONNAIRE

DEVICE PROCEDURE QUESTIONNAIRE

ENSEAL® X1 Large Jaw Tissue Sealer

Surgeon's (Printed) Name: _____

Procedure Date: _____

Subject #: _____

1. Was the transection of the vessels by the ENSEAL® X1 device performed with just one hand or were two hands needed at any time to complete it:

One hand Two hands

If two hands were used, please describe:

2. Did the ENSEAL® X1 device have to be removed and then put back into the surgical field during the transection of the vessels for repositioning or adjustment:

Yes No

If yes, please describe and list how many times this was done:

3. Was there a need to change hand positions to activate the ENSEAL® X1 device during the transection of the vessels:

Yes No

If yes, please explain:

APPENDIX III – SURGEON QUESTIONNAIRE

SURGEON QUESTIONNAIRE

ENSEAL® X1 Large Jaw Tissue Sealer (ENSEAL® X1)

Surgeon's (Printed) Name: _____

Glove Size: _____

Procedure Date: _____

1. The ENSEAL® X1 device was better balanced compared to previous advanced bipolar device use:

Strongly disagree Slightly disagree Neutral Slightly agree Strongly agree

Comments: _____

2. You experienced less hand fatigue using the ENSEAL® X1 device compared to previous advanced bipolar device use:

Strongly disagree Slightly disagree Neutral Slightly agree Strongly agree

Comments: _____

3. The buttons were easily distinguishable on the ENSEAL® X1 device:

Strongly disagree Slightly disagree Neutral Slightly agree Strongly agree

Comments: _____

4. The firing (sealing/cutting) of the ENSEAL® X1 device was easier compared to previous advanced bipolar device use:

Strongly disagree Slightly disagree Neutral Slightly agree Strongly agree

Comments: _____

APPENDIX IV – ANTICIPATED ADVERSE EVENTS

Associated with General Anesthesia, Thoracic Surgery, Colectomy Surgery, and Gynecological Surgery

Abscess	Infertility
Acute respiratory distress syndrome	Intercostal nerve injury
Adhesions	Ischemia
Air/gas embolism	Jaundice
Altered mental status	Leak
Anaphylaxis	Lethargy
Anastomotic leak	Leukocytosis
Anemia	Liver failure
Angina	Mesenteric infarct
Atelectasis	Mesenteric ischemia
Bacteremia	Myocardial infarction
Bladder injury	Nausea
Bleeding	Nerve injury
Bowel/bladder urgency or incontinence	Nutrient deficiency
Bowel obstruction	Obtundation, depressed levels of consciousness
Bradycardia	Oliguria
Broncho pleural fistula	Pain (increased/severe/chronic)
Cardiac arrhythmia	Peritonitis
Central line infection	Pneumonia
Cerebrovascular accident/stroke	Pneumothorax
Chylothorax	Premature menopause
Congestive heart failure	Prolonged air leak
Constipation	Pulmonary air leak
Deep venous thrombosis	Pulmonary embolism
Dehydration	Renal failure
Dementia	Respiratory failure
Diaphragmatic injury	Respiratory insufficiency
Diarrhea	Sepsis
Discharge of feces through drain	Sexual dysfunction (or erectile/ejaculatory dysfunction)
Disseminated intravascular coagulation (DIC)	Somnolence
Dizziness	Stricture
Dysphagia	Systemic inflammatory response syndrome
Dyspareunia	Tachycardia
Electrolyte imbalance	Thoracic duct injury
Empyema	Thromboembolic event
Esophageal injury	Tightness of the chest
Evisceration	Thrombocytopenia
Fever, pyrexia	Thromboembolic event
Fistula	Thrombosis
Headache	Transient ischemic attack
Hematuria	Tightness of the chest, angina
Hemorrhage	Tinnitus
Hemothorax	Urinary retention
Hernia	Urinary tract infection
Hypematremia	Ureteric injury
Hyperphosphatemia	Vaginal cuff dehiscence
Hypertension	Vascular injury
Hypotension, shock	Volume depletion, hypovolemia
Hypoxia	Vomiting
Ileus	Wheezing
Incisional hernia	Wound dehiscence
Infection/SSI/abscess	Wound infection

# 1 Introduction

This is the Statistical Analysis Plan (SAP) for the final analysis of data collected under Protocol ENG-17-001. This SAP describes in detail the statistical methodology and statistical analyses for this protocol.

## 1.1 Study Objectives

The primary objective of this study is to prospectively generate device-specific clinical data related to hemostasis in a post-market setting using the ENSEAL X1 device per its Instruction For Use (IFU). Secondary objectives include proactive surveillance of safety and performance outcomes following use of the ENSEAL X1.

## 1.2 Study Design

This is a prospective, single-arm, multi-center evaluation designed to collect clinical data in a post-market setting for colectomy, gynecological, and thoracic procedures. Investigators will perform each procedure using the device in compliance with their standard surgical approach and the ENSEAL X1 IFU.

Each site will utilize consecutive screening and enrollment in an effort to generate a random and representative patient population sample. Subjects will be consented and screened anytime between the time of scheduling the procedure and hospital admission (this period will vary per subject but may occur over several dates within an 8-week period prior to surgery). Subjects will be considered enrolled at the time of the first attempted vessel transection using the ENSEAL X1 device during their procedure. Procedures will be performed per each institution's standard-of-care (SOC) that is specific for each procedure group (colectomy, gynecological, and thoracic). The last study visit will be at the post-op follow-up visit at approximately 4 weeks. Follow-up by phone for subjects is allowed when an on-site visit is not planned.

A total of 100 eligible subjects were planned to be enrolled with a minimum of 30 subjects enrolled for colectomy procedures (e.g., total colectomy, partial colectomy, hemicolectomy, proctocolectomy), a minimum of 30 subjects enrolled for gynecological procedures (e.g., hysterectomy), and a minimum of 20 subjects enrolled for thoracic procedures (e.g., esophagectomy). The remaining 20 subjects could be enrolled from any of the three procedure groups and enrollment will be competitive between procedure groups.

# 2 Treatment Assignment

This is a single-arm study where all enrolled subjects will have the ENSEAL X1 device utilized for transection of at least one vessel.

### **3 Randomization and Blinding Procedures**

As this is a single-arm study, no randomization occurred, and no blinding procedures are required.

### **4 Interval Windows**

Interval windows for the purpose of analysis in this study are not defined outside of those already specified in the protocol for visit scheduling as the collection of data for the primary and secondary performance endpoints occurs intra-operatively. The final visit occurs approximately 4 weeks after surgery, thus no interval windows for analysis need to be defined given the absence of long-term follow-up in this study. The protocol Schedule of Events specifies a window of 14 days around the scheduling of the 4-week follow-up visit, and any information entered in the electronic Case Report Forms (eCRFs) at this visit will correspond to the 4-week visit. There will be no assigning of observations to time points outside of the visit to which they are recorded in the eCRFs.

### **5 Levels of Significance**

No hypotheses are specified for this study and no p-values are being calculated, therefore no level of significance is specified. All estimation of endpoints will be performed using 95% confidence intervals.

### **6 Analysis Sets**

The summary of all performance and safety endpoints will be performed on the set of subjects in whom the ENSEAL X1 device is utilized during the surgical procedure. This will be labeled the ENSEAL Analysis Set. This set of subjects will be identified by having at least one entry in the Vessel Transected eCRF or by having answered “Yes” to the question “Was ENSEAL X1 used for tissue cutting or dissection?” on the Intra-Operative Data eCRF. The summary of all primary and secondary performance endpoints will be performed by procedure group (colectomy, gynecological, or thoracic). The summary of all safety endpoints will be performed by procedure group and on the entire pooled set of subjects.

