3.2 STUDY POPULATION

3.2.1 Enrollment

Subjects will be recruited from the existing patient population who plan to have an elective procedure from the proposed procedure groups (colectomy, gynecological, and thoracic). All eligible subjects (Sections 3.2.3 and 3.2.4) will be considered enrolled at the time of the first attempted vessel transection using the ENSEAL X1 device during their procedure. Up to 8 centers (United States and Europe) will be selected as study sites. Each participating investigator is expected to perform a minimum of two procedures using the ENSEAL X1 device. A total of 100 eligible subjects are planned to be enrolled with a minimum of 30 subjects enrolled for colectomy procedures (e.g., total colectomy, partial colectomy, hemicolectomy, proctocolectomy), a minimum of 30 subjects enrolled for gynecological procedures (e.g., hysterectomy), and a minimum of 20 subjects enrolled for thoracic procedures (e.g., esophagectomy). The remaining subjects will be enrolled from any of the three procedure groups and enrollment will be competitive between procedure groups and the remaining 20 subjects.

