3.2.2 Screening Failures

All subjects signing consent who do not have at least one vessel transection attempted by ENSEAL X1 during their procedures will be recorded as screen failures. For subjects who are determined to be screen failures, only the relevant electronic eCRF pages (inclusion/exclusion criteria, demographics, AEs, subject completion/discontinuation) will be completed.

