### 8.7 Handling of Missing Data

All summaries will be performed only on enrolled subjects and only observed data will be summarized. There will be no imputation of data for early terminated subjects or for missing data within the database.

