System Organ Class 4		xx (xx.x%)	xx (xx.x%)	xx (xx.x%)	xx (xx.x%)
	Preferred Term 1	xx (xx.x%)	xx (xx.x%)	xx (xx.x%)	xx (xx.x%)
	Preferred Term 2	xx (xx.x%)	xx (xx.x%)	xx (xx.x%)	xx (xx.x%)

The following tables will have the same format as Table 14:

Table 15	All Serious Adverse Events by System Organ Class and Preferred Term ENSEAL Analysis Set
Table 16	Adverse Events Related to the Study Device by System Organ Class and Preferred Term ENSEAL Analysis Set
Table 17	Serious Adverse Events Related to the Study Device by System Organ Class and Preferred Term ENSEAL Analysis Set
Table 18	Adverse Events Related to the Study Procedure by System Organ Class and Preferred Term ENSEAL Analysis Set
Table 19	Serious Adverse Events Related to the Study Procedure by System Organ Class and Preferred Term ENSEAL Analysis Set

Table 20  
Protocol Deviations  
ENSEAL Analysis Set

Characteristics	Colectomy (N = ##)	Gynecological (N = ##)	Thoracic (N = ##)	Total (N = ##)
Total Number of Protocol Deviations	xxx	xxx	xxx	xxx
Specific Types of Protocol Deviations [1]				
Informed Consent Process	xx (xx.x%)	xx (xx.x%)	xx (xx.x%)	xx (xx.x%)
Inclusion/Exclusion Criteria	xx (xx.x%)	xx (xx.x%)	xx (xx.x%)	xx (xx.x%)
Study Procedure	xx (xx.x%)	xx (xx.x%)	xx (xx.x%)	xx (xx.x%)
Visit Out of Window	xx (xx.x%)	xx (xx.x%)	xx (xx.x%)	xx (xx.x%)
Other	xx (xx.x%)	xx (xx.x%)	xx (xx.x%)	xx (xx.x%)
Sponsor Assessment of Protocol Deviations [1]				
Minor	xx (xx.x%)	xx (xx.x%)	xx (xx.x%)	xx (xx.x%)
Major	xx (xx.x%)	xx (xx.x%)	xx (xx.x%)	xx (xx.x%)
Number (%) of Subjects With at Least 1 Protocol Deviation [2]	xx (xx.x%)	xx (xx.x%)	xx (xx.x%)	xx (xx.x%)

1. Denominator used is the total number of protocol deviations reported.
2. Denominator used is the total number of subjects in the column header.

Table 21  
Summary of Vessel Categorization  
ENSEAL Analysis Set

Procedure Group Vessel Name	Colectomy (M = ##)	Gynecological (M = ##)	Thoracic (M = ##)
Colectomy			
IMA	xx (xx.x%)		
IMV	xx (xx.x%)		
Ileocolic	xx (xx.x%)		
Middle colic	xx (xx.x%)		
Right colic	xx (xx.x%)		
Sigmoid	xx (xx.x%)		
Gynecological			
Right uterine		xx (xx.x%)	
Left uterine		xx (xx.x%)	
Right ovarian		xx (xx.x%)	
Left ovarian		xx (xx.x%)	
Omental		xx (xx.x%)	
Thoracic			
Short gastric			xx (xx.x%)
Left gastroepiploic			xx (xx.x%)
Left gastric			xx (xx.x%)

Column header, M, is the total number of vessel transections in the given group and serves as the denominator for calculation of percentages in the table.

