*Programming note: Data is sourced from external file where vessel categorization is performed based on free text field entries in the Vessel Transected CRF. Additional categories beyond those presented above may be included.*

The following listings will be generated for this study:

Listing 1	Inclusion/Exclusion Criteria All Subjects
Listing 2	Demographics All Subjects
Listing 3	Vital Signs All Subjects
Listing 4	Medical History All Subjects
Listing 5	Surgical History All Subjects
Listing 6.1	Background Information 1 (Part 1) All Subjects
Listing 6.2	Background Information 1 (Part 2) All Subjects
Listing 7	Background Information 2 All Subjects
Listing 8.1	Intra-Operative Data (Part 1) All Subjects
Listing 8.2	Intra-Operative Data (Part 2) All Subjects
Listing 9	Vessel Transected All Subjects
Listing 10	Grade 4 Page All Subjects
Listing 11	Device Log All Subjects
Listing 12	Device Procedure Questionnaire All Subjects

Listing 13	Blood Transfusion Detail All Subjects
Listing 14	Chest Tube Detail All Subjects
Listing 15.1	Surgeon Questionnaire (Part 1) All Subjects
Listing 15.2	Surgeon Questionnaire (Part 2) All Subjects
Listing 16	Discharge All Subjects
Listing 17	Visual Analog Scale All Subjects
Listing 18	Subject Completion/Discontinuation All Subjects
Listing 19	Protocol Deviations All Subjects
Listing 20	Concomitant Procedures All Subjects
Listing 21	Concomitant Medications All Subjects
Listing 22	Adverse Events All Subjects
Listing 23	Study Visits All Subjects

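### SAP 6 counts a subject with cutting- or dissection-only ENSEAL X1 use in the safety set, but Protocol 3.2.2 and SAP 8.7 leave that subject out

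*SAP*

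**What the plan says.** SAP 6 (Analysis Sets) bases all performance and safety summaries on subjects in whom ENSEAL X1 was used during surgery, and Protocol 4.5.6 uses the same idea. SAP 6 calls this the ENSEAL Analysis Set. A subject enters through at least one Vessel Transected entry or, alternatively, "by having answered “Yes” to the question “Was ENSEAL X1 used for tissue cutting or dissection?” on the Intra-Operative Data eCRF".

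Protocol 3.2.2 (Screening Failures) says that consented subjects "who do not have at least one vessel transection attempted by ENSEAL X1 during their procedures will be recorded as screen failures". For them, "only the relevant electronic eCRF pages (inclusion/exclusion criteria, demographics, AEs, subject completion/discontinuation) will be completed". Protocol 3.2.1 fixes enrolment by the same event: eligible subjects "will be considered enrolled at the time of the first attempted vessel transection using the ENSEAL X1 device during their procedure". SAP 1.2 repeats this.

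SAP 8.7 (Handling of Missing Data) adds: "All summaries will be performed only on enrolled subjects". The matching Protocol section, 4.5.9.6, is worded differently: "All summaries will be performed only on subjects undergoing the scheduled procedure".

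In the SAP Appendix, Tables 14 to 19 are headed with the ENSEAL Analysis Set. Table 16 is "Adverse Events Related to the Study Device by System Organ Class and Preferred Term", and SAP 8.5 makes device-related events the primary safety endpoint. Listing 22 is "Adverse Events All Subjects".

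**The concern.** Cutting and dissecting tissue are intended uses of the device (Protocol 3.3.2.2), and the study records them (Protocol 3.4.2). A subject exposed to the device in this way, with no vessel transection attempted, can have a device-related adverse event. The second route into the ENSEAL Analysis Set seems meant to keep such a subject in the safety summaries. Protocol 3.2.2 and SAP 8.7 work against it.

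What is at stake is the completeness of the primary safety table. An event in such a subject would be collected and listed, but not counted in the tabulated device-related events. Table 1 would not reveal this. It gives the number consented and the number in the ENSEAL Analysis Set, but has no row for screen failures or for device use among them.

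**Working it through.** **Following one subject through the rules.** Take a consented subject in whom ENSEAL X1 is used to dissect tissue and no vessel transection is attempted.

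1. SAP 6: the device was used, so the subject meets the definition and qualifies by the second route.
2. Protocol 3.2.1: no transection was attempted, so the subject is not enrolled.
3. Protocol 3.2.2: the subject is a screen failure. The pages listed are inclusion/exclusion criteria, demographics, AEs and completion/discontinuation. Intra-Operative Data is not listed, so the answer SAP 6 relies on is not recorded.
4. SAP 8.7: even if a site did complete that page, the restriction to enrolled subjects would remove the subject. This conflict is separate from step 3.
5. Protocol 5.2.2 requires AE reports for subjects who gave consent, and the AE page is on the screen-failure list. The event therefore reaches Listing 22.
6. Tables 14 to 19 use the ENSEAL Analysis Set. With the page missing (step 3) or the subject excluded (step 4), the event is in none of them.

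**The plan's own figures.** SAP 7 gives two numbers for 100 subjects, and both reproduce:

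- Probability of at least one event at a 2% rate: 1 − 0.98^100 = 0.8674, stated as 86.7%.
- Exact two-sided 95% upper limit for 0/100: 1 − 0.025^(1/100) = 3.62%, stated as less than 3.7%.

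Both refer to the 100 enrolled subjects. The subject in question is not one of them, so neither figure changes.

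**Effect on a displayed count.** The documents give no number of such subjects, so k is an assumption. Enrolled numbers are the planned 100, and the group minimums of 30 (colectomy, gynecological) and 20 (thoracic), from Protocol 3.2.1. Suppose that one of the k omitted subjects has the only event of a given type:

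| Setting | Shown under the current rules | With device-exposed subjects included |
|---|---|---|
| Pooled, k = 1 | 0/100 = 0.0% | 1/101 = 0.99% |
| Pooled, k = 5 | 0/100 = 0.0% | 1/105 = 0.95% |
| Pooled, k = 10 | 0/100 = 0.0% | 1/110 = 0.91% |
| Colectomy or gynecological, k = 1 | 0/30 = 0.0% | 1/31 = 3.2% |
| Thoracic, k = 1 | 0/20 = 0.0% | 1/21 = 4.8% |

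If the omitted subject had no event and one enrolled subject did, the rate goes from 1/100 = 1.00% to 1/101 = 0.99%. Both print as 1.0% at the one decimal place in the shell. The bias can therefore run either way: an omitted event lowers the reported rate, and an omitted event-free subject raises it very slightly.

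**The case against.** The best defence is that the case may never arise. Inclusion criterion 1 (Protocol 3.2.3) requires a planned ENSEAL X1 vessel transection, and nothing in the documents shows a subject with dissection-only use. This stands. It limits the size of the point but does not reconcile the rules.

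A second defence is that SAP 8.7 and Protocol 4.5.9.6 are missing-data sections meant to rule out imputation, and that the table headings show SAP 6 governs. That is a fair reading, and the wording of Protocol 4.5.9.6 is better seen as loose than as a deliberate further population. But if SAP 6 governs, the page it needs is still not completed for a screen failure.

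Third, other outputs may show the exposure. Listing 11 (Device Log) and Listings 8.1 and 8.2 (Intra-Operative Data) cover all subjects. The Device Log's content is not shown. The Intra-Operative listings cannot help where the page was never completed.

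Three stronger readings are tempting but not supported:

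- A reader might infer that the omission undermines SAP 7's limit of 3.7%, because one event raises the exact upper limit to about 5.4%. That rise comes from seeing one event at all: 1/100 also gives about 5.4%. SAP 7's figure is a planning statement conditional on zero events, and the AE shells show no confidence intervals.
- A reader might infer that enrolled subjects whose attempted transections all failed also drop out of the analysis set. That depends on whether attempts are entered on the Vessel Transected form, which the documents do not show.
- A reader might infer that events are lost. They are not: they are collected and listed.

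**Conclusion.** The inconsistency is real and lies in the current text of both documents. SAP 6 includes a subject with cutting- or dissection-only use. Protocol 3.2.2 withholds the page that would identify the subject, and SAP 8.7 excludes anyone not enrolled. Following the stated rules gives a safety population narrower than the one SAP 6 defines.

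The consequence depends on two conditions: that such a subject occurs, and that sites and programmers follow the rules as written. Then a device-related event would be in Listing 22 and absent from Tables 14 to 19, including Table 16. The number affected is unknown and probably small, and the effect on a displayed count is of the order of 0/100 instead of 1/101. The primary performance endpoint is not affected, because these subjects contribute no transections. Severity is minor.

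**What to change.** - **SAP 6:** state that the safety set is every consented subject with any ENSEAL X1 use, meaning an attempted or completed transection, or cutting or dissection.
- **SAP 8.7:** replace the reference to enrolled subjects with the ENSEAL Analysis Set.
- **Before the safety tables are produced:** check source records, and the Device Log if it records this, for device use among screen failures. If there was none, one sentence in the report closes the matter.
- **SAP Table 1:** add a row for screen failures with device use.
- **Protocol 3.2.2, only if enrolment is still open:** require the existing Intra-Operative Data page, and the page that records procedure group, for any device-exposed subject. Procedure group is needed to place the subject in a column of Tables 14 to 19.

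The primary performance analysis and Table 7 stay as they are.

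The cost is two SAP wording changes, one table row and a small record check. A change to Protocol 3.2.2 may need IRB/EC approval before it is implemented (Protocol, Administrative Requirements, Protocol Modifications), because extra data collection is not clearly an administrative change. For past screen failures, Visit 3 data may be incomplete and this should be stated. The reported adverse event rate may differ slightly from that under the current rules.
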